1.4 Subgroups

Per the 2009 Institute of Medicine guidelines, each BMI category is allocated a different rate of GWG per week [1]. Therefore, intervention effects within each body mass index (BMI) category (normal weight, overweight, obesity) will be determined as a subgroup analysis. The study sample sizes are powered to detect differences within each subgroup.

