The sample size was updated to a minimum of 330. The initial estimated effect size for the SmartMoms® intervention was based on preliminary data in the Expecting Success trial. The incidence of appropriate GWG for people with overweight was 12.3% for Usual Care versus 43.8% in SmartMoms®, and in people with obesity, it was 0% for Usual Care and 42.9% in SmartMoms®. However, the Expecting Success trial was not conducted in an exclusively underserved population, so we needed to conservatively estimate the SmartMoms® intervention effect to ensure this study would be well powered. The incidence of appropriate GWG for the Usual Care group was derived from individuals receiving WIC benefits in the 2013 Louisiana Pregnancy Risk Assessment Monitoring System data. The table below was created to show the incidences needed for 80% power in each of the BMI categories. All the estimates were tenable since they were lower than the SmartMoms® trial estimates. This study aimed for a total sample of 432 originally to allow for unknown variability that may have caused the observed rates to be different than the ones used for the power analysis. Sample size was reassessed in response to the COVID-19 pandemic. Based on the feasible recruitment estimates, the sample size was lowered to a minimum of 330. No new data were used to obtain the changes in power.

Table 1. Sample Size Estimates

BMI Category	Usual Care Appropriate GWG Incidence Rate	SmartMoms® Appropriate GWG Incidence Rate				
Normalweight	36.9	50.9	51.4	51.9	52.4	52.9
Overweight	23.9	37.9	38.4	38.9	39.4	39.9
Obesity	25.2	39.2	39.7	40.2	40.7	41.2
Overall	28.7	42.7	43.2	43.7	44.2	44.7
Sample Size		432	405	372	350	330

Section 3.0

Amendment May 2024:

Section was rewritten to clarify that treatment group differences within each BMI category is an apriori subgroup analysis we would consider.

Section 3.1

Amendment May 2024:

Description of methodology used to assess distributional assumptions was reduced to allow for which test is most statistically appropriate to be used.

Section 3.3

Amendment May 2024:

Based on recommendation from other statistical analysis experts in maternal health, a priori variable selection for determining covariates will be used. Gestational age at randomization, BMI category at randomization, and categorically defined parity will be the only covariates to be included in the model. Exploratory analysis will examine relationships of the outcomes with other

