2.3 Sample Size and Study Power

Study hypotheses will be assessed using appropriate statistical tests, input variables and endpoints, and therefore, power calculations and sample size estimates are presented for the study aims. Estimates of the study power are derived from our preliminary data and from existing literature. The 1:1 randomization scheme within each BMI stratum is applied to ensure that the study is also sufficiently powered to compare intervention effectiveness within BMI groups which is important for the program announcement (PA-18-135).

The sample size estimates assume β =0.8 and α =0.05 to detect the specified differences between incidence rates of appropriate GWG. All sample sizes are inflated to account for 15% attrition. Intent-to-treat (ITT) analyses will be used. Participants are required to have at least one follow-up clinic weight to compute GWG (incidence rate, study observed, per week, and deviation). We plan to enrol at least 330 participants, with relative balance within each BMI stratum. We have sufficient power for our primary comparisons of GWG as well as comparisons within BMI groups. Due to the Covid-19 pandemic impacting trial procedures and enrolment, the goal of this study is to enrol at least 330 participants. That is, the study will continue to enrol individuals until either the end of the enrolment period (December 2023, with participants having to be certified to receive WIC benefits by October 31, 2023, to be eligible) or until all three BMI categories have 110 enrolled participants. Enrolment in any given BMI category will continue past 110 if the other BMI categories have yet to meet the enrolment goal.

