2.3.1 Sample Size Estimates for Specific Aims

Hypothesis 1: The incidence of appropriate study observed GWG per week according to the 2009 Institute of Medicine guidelines¹ will be higher in the SmartMoms® group as compared to the Usual Care group.

The estimated incidences of appropriate GWG for the Usual Care group were derived from data based on pregnant individuals receiving WIC benefits in the 2013 Louisiana Pregnancy Risk Assessment Monitoring System.² The estimated effect size for the SmartMoms® intervention is based on preliminary data from our Expecting Success trial where the incidence of appropriate GWG for pregnant individuals with overweight was 12.3% for Usual Care versus 43.8% in SmartMoms®; and for pregnant individuals with obesity, 0% for Usual Care and 42.9% in SmartMoms®. However, since Expecting Success³ was not conducted in an exclusively underserved population, we conservatively estimated that the SmartMoms® intervention would increase the incidence by a minimum of 16% across BMI categories. The resulting overall incidence would be similar to our observation in Expecting Success (Table 1). To observe a 16% difference in the incidence between SmartMoms® and Usual Care while accounting for 15% attrition, at least 330 participants with 1:1 allocation between the two groups and equal stratification within each BMI stratum is required.

Table 1. Sample Size Estimates

BMI Category	Usual Care Appropriate GWG Incidence Rate	SmartMoms® Appropriate GWG Incidence Rate				
Normalweight	36.9	50.9	51.4	51.9	52.4	52.9
Overweight	23.9	37.9	38.4	38.9	39.4	39.9
Obesity	25.2	39.2	39.7	40.2	40.7	41.2
Overall	28.7	42.7	43.2	43.7	44.2	44.7
Sample Size		432	405	372	350	330

In additional to overall differences in incidence of appropriate GWG, this study is also powered to detect incidence differences within each BMI stratum. Assuming an overall difference in incidence of 16%, 110 participants in each BMI stratum are sufficient to detect a difference of at 26% in incidence within each BMI stratum (Table 2).

Table 2. Power For Detecting Differences Within Each BMI Stratum

Difference in Incidence	Power
23%	0.70
26%	0.80
29%	0.88

Hypothesis 2: Study observed GWG seen in the SmartMoms® group will be less as compared to the Usual Care group. This will be assessed using the following three measures: study-observed GWG, weekly GWG, and deviation from the 2009 Institute of Medicine guidelines.¹

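### For the incidence outcome, the SAP's unqualified claim of power within each BMI subgroup does not hold at its own 16-point planning effect (about 34–44% power), and Table 2's 80% at 26 points leaves out the stated attrition

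*SAP*

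**What the plan says.** SAP 1.4 sets up treatment effects within normal weight, overweight and obesity as a subgroup analysis and states: "The study sample sizes are powered to detect differences within each subgroup". SAP 2.3 says: "We have sufficient power for our primary comparisons of GWG as well as comparisons within BMI groups". Neither sentence names an effect size.

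SAP 2.3.1 sets the planning effect for Hypothesis 1 at a minimum of 16 points across BMI categories. The 330-participant column of Table 1 applies exactly that gain in each one: 36.9% to 52.9% (normal weight), 23.9% to 39.9% (overweight), 25.2% to 41.2% (obesity) and 28.7% to 44.7% overall.

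The same section then ties stratum power to a larger effect: "110 participants in each BMI stratum are sufficient to detect a difference of at 26% in incidence within each BMI stratum". Table 2 lists power of 0.70, 0.80 and 0.88 for differences of 23, 26 and 29 points. On attrition, SAP 2.3 says: "All sample sizes are inflated to account for 15% attrition".

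SAP 4.3 plans to run and report the Hypothesis 1 analysis within each BMI category.

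**The concern.** A reader of SAP 1.4 and 2.3 will take subgroup power to refer to the effect on which the trial is planned. That effect is 16 points in every stratum, and Table 2 shows that 80% power in a stratum of 110 needs 26. The unqualified sentences thus suggest a property that the design lacks at its own planning effect.

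Table 2 also appears to use all 110 enrolled participants, although SAP 2.3 says attrition is built into every sample size. SAP 3.4 rules out imputation, and the primary analysis in SAP 4.1 uses the early and late pregnancy visits, so lost participants do reduce the number analysed.

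The stake is interpretation. If the planned effect is exactly true, each stratum is more likely than not to be non-significant. Readers told that the strata were powered could take such a result as evidence that SmartMoms does not work in that BMI group, in a trial meant to inform wider use in WIC.

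**Working it through.** **Inputs.** α = 0.05 and target power 80% (SAP 2.3, which writes the target as β = 0.8); 1:1 allocation within strata (SAP 2.3); 15% attrition (SAP 2.3); rates from SAP Table 1; 110 per stratum (SAP 2.3.1). The SAP does not state sidedness; two-sided is assumed because it reproduces both tables.

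**Formula.** Two proportions p1 and p2, n per arm, Δ = p2 − p1, p̄ = (p1 + p2)/2:

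power = Φ{ [Δ − 1.96·√(2p̄(1−p̄)/n)] / √[(p1(1−p1) + p2(1−p2))/n] }

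Per arm, n = 110/2 = 55 if all are analysed, and 55 × 0.85 = 46.75 after attrition.

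**Step 1: Table 1 (overall).** For 28.7% vs 44.7%, 330 × 0.85 / 2 = 140.25 per arm. Then p̄ = 0.367, and (0.16 − 1.96 × 0.0576)/0.0568 = 0.83, so power is 79.7%. The 330 reproduces for the overall comparison, with attrition included.

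**Step 2: Table 2 (within a stratum).** Control rate 28.7%:

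| Difference | SAP Table 2 | n = 55 | n = 46.75 |
|---|---|---|---|
| 23 points | 0.70 | 0.696 | 0.624 |
| 26 points | 0.80 | 0.798 | 0.729 |
| 29 points | 0.88 | 0.877 | 0.819 |

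For example, 26 points at n = 55 gives (0.26 − 1.96 × 0.0940)/0.0907 = 0.83, so 0.798. At n = 46.75 it gives (0.26 − 1.96 × 0.1020)/0.0984 = 0.61, so 0.729. With the stratum-specific control rates, power at 26 points after attrition is 0.717 (normal weight), 0.749 (overweight) and 0.742 (obesity).

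The choice of test does not explain the gap. At about 47 per arm, 26 points and a 28.7% control rate, unpooled, arcsine, continuity-corrected and Fisher exact versions give 0.66–0.76. A one-sided test gives 0.83, and it would put the overall sample size in Table 1 at 264, not 330. Table 2 therefore assumes no attrition, unlike Table 1.

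**Step 3: stratum power at the planned 16 points.**

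| Stratum | Rates | n = 55 | n = 46.75 |
|---|---|---|---|
| Normal weight | 36.9% vs 52.9% | 39.1% | 34.1% |
| Overweight | 23.9% vs 39.9% | 43.6% | 38.0% |
| Obesity | 25.2% vs 41.2% | 42.8% | 37.4% |

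For example, normal weight at n = 55 gives (0.16 − 1.96 × 0.0949)/0.0936 = −0.28, so 39.1%. One-sided power at 16 points would be 46–56%, still well below 80%.

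**Step 4: what 80% would need.** At 16 points, the same formula solved for n gives 151, 133 and 135 per arm. Allowing for attrition, that is 302/0.85 = 356, 266/0.85 = 313 and 270/0.85 = 318 per stratum, against 110. Conversely, with 46.75 per arm and a 28.7% control rate, 80% power needs about 28.3 points: (0.283 − 1.96 × 0.1024)/0.0981 = 0.84.

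**The case against.** The best defence is that power always depends on an effect size, and the SAP gives it. Section 2.3.1 ties stratum power to 26 points, Table 2 gives the curve, and on enrolled numbers it is correct. The 16 points is called a conservative minimum, so a larger detectable difference in a subgroup does not by itself contradict the plan. This stands. A reader might infer that the subgroup power claim is simply false; the documents do not support that, because 1.4 names no effect and 2.3.1 names one openly.

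A reader might also infer that 26 points is untenable, since adding it to the Usual Care planning rates gives 49.9% (overweight) and 51.2% (obesity), above the pilot SmartMoms rates of 43.8% and 42.9%. That comparison mixes pilot treatment rates with control rates from another source. On the difference scale that Table 2 uses, the pilot showed 43.8 − 12.3 = 31.5 points and 42.9 − 0 = 42.9 points, both above 26. The SAP's remark about tenable estimates concerns Table 1, and there is no pilot rate for normal weight.

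The amendment entry for Section 2.3 says "The table below was created to show the incidences needed for 80% power in each of the BMI categories". It could be read as claiming 80% in every stratum, or as listing the per-category incidences that give 80% overall. It sits in the amendment log, and nothing here rests on it.

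Finally, SAP 3 asks for point estimates, confidence intervals and a caution for secondary and exploratory outcomes. That helps, but it does not name subgroup results on the primary outcome.

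What the defence leaves standing is that 1.4 and 2.3 carry no qualification, stratum power at the planning effect appears nowhere, and Table 2 leaves out attrition.

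**Conclusion.** For Hypothesis 1, the statements in SAP 1.4 and 2.3 are misleading as written. At the planned 16-point effect, power within a BMI stratum of 110 is about 39–44% with all analysed and about 34–38% after 15% attrition. The 80% in Table 2 belongs to a 26-point difference with no attrition; with attrition it is about 73% (72–75% across strata).

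This assumes a two-sided 0.05 test, the Table 1 rates and exactly 110 per stratum. SAP 2.3 allows a category to pass 110, or enrolment to close before every category reaches it, so actual power could differ either way. Closing a gap to 313–356 per stratum would take far more than a modest excess over 110.

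The overall comparison is unaffected. Nor does the finding extend to all within-BMI claims: SAP 2.3.1 also claims more than 80% power for 0.16 kg/week within each BMI category, and without a standard deviation that can be neither confirmed nor rejected.

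**What to change.** Change the wording of the SAP only:

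- In 1.4 and 2.3, limit the statement for incidence of appropriate GWG. Say that the sample size is powered for the overall comparison; that power within a BMI stratum is about 34–38% at the planned 16-point effect after attrition; and that about 80% needs a 26-point difference with no attrition, or a larger one (about 28 points at the 28.7% control rate) with it.
- Restate Table 2 after attrition as about 0.62, 0.73 and 0.82 at 23, 26 and 29 points, or label it as assuming no attrition.
- In 4.3, report the stratum results for Hypothesis 1 as estimates with 95% confidence intervals, and state that a non-significant stratum is not evidence of no effect.
- Leave the 0.16 kg/week subgroup claim out of this correction.

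This needs no extra participants and no change to the primary analysis. The cost is that a stated property of the design becomes less favourable.

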1.5 Exploratory Aims

We designed the research program such that our primary objectives, described above, are the foundation of a rigorously designed study with mechanistic hypotheses. Such a study design requires focus and derivation of hypotheses that are strongly supported by preliminary data and adequate study power. Through this process, we identified many promising hypotheses that did not meet our rigorous criteria for being a primary outcome. Pregnancy and birth outcomes are of great significance but have less supporting evidence and we therefore classified them as exploratory outcomes.

2 STUDY METHODS

This study will be using a parallel-arm design with one intervention arm (SmartMoms®) and one control arm (Usual Care). Each participant will be followed for approximately 24 weeks (from week 16 until delivery). Measurements on the primary outcomes will be collected in clinic visits occurring at early (10,0 to 16,6 weeks gestation), mid (24,0 to 27,6 weeks), and late (35,0 to 37,6 weeks) pregnancy.

2.1 Study Sample

At least 330 pregnant individuals certified to receive WIC services during the current pregnancy (had to be certified by October 31, 2023) will be enrolled from WIC clinics across the nine Louisiana Department of Health (LDH) regions.

Eligible participants will satisfy the following inclusion criteria:

1) Aged 18-40 year,

- 2) BMI 18.5-40.0 kg/m²,
- 3) Expecting a singleton pregnancy,
- 4) No current mental health issue or eating disorder,
- 5) Not planning to move out of the area in the next 18 months.

Participants will be excluded for:

- 1) History of or current smoking, drug or alcohol use,
- 2) Significant non-pregnancy related illness (HIV, cancer, heart disease, diabetes),
- 3) Inability to complete the behavioral run-in task.

2.2 Randomization

Individuals will be randomized 1:1 to either the SmartMoms® or Usual Care group. Prior to randomization, the participant and study staff will review a document that outlines behavioral requirements for each group and affirms responsibilities during the study. Once the participant confirms understanding of study requirements, randomization will occur via a phone call with intervention staff. The randomization schedule will be prepared by the study statistician and use a permuted block strategy with stratification for LDH region (1 through 9) and BMI category (normal weight, overweight, obesity) to ensure balance within each stratum between individuals in the SmartMoms® or Usual Care groups. The Research Electronic Data Capture (REDCap) will be used to conceal the allocation sequence to intervention staff until randomization occurs.

2.3 Sample Size and Study Power

Study hypotheses will be assessed using appropriate statistical tests, input variables and endpoints, and therefore, power calculations and sample size estimates are presented for the study aims. Estimates of the study power are derived from our preliminary data and from existing literature. The 1:1 randomization scheme within each BMI stratum is applied to ensure that the study is also sufficiently powered to compare intervention effectiveness within BMI groups which is important for the program announcement (PA-18-135).

The sample size estimates assume β =0.8 and α =0.05 to detect the specified differences between incidence rates of appropriate GWG. All sample sizes are inflated to account for 15% attrition. Intent-to-treat (ITT) analyses will be used. Participants are required to have at least one follow-up clinic weight to compute GWG (incidence rate, study observed, per week, and deviation). We plan to enrol at least 330 participants, with relative balance within each BMI stratum. We have sufficient power for our primary comparisons of GWG as well as comparisons within BMI groups. Due to the Covid-19 pandemic impacting trial procedures and enrolment, the goal of this study is to enrol at least 330 participants. That is, the study will continue to enrol individuals until either the end of the enrolment period (December 2023, with participants having to be certified to receive WIC benefits by October 31, 2023, to be eligible) or until all three BMI categories have 110 enrolled participants. Enrolment in any given BMI category will continue past 110 if the other BMI categories have yet to meet the enrolment goal.

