3. BACKGROUND AND SIGNIFICANCE

Pregnancy is critical nutritional time point that influences the immediate and long-term health of both mother and child. While the health and nutritional status of women (eg. obesity, smoking etc.) prior to pregnancy is arguably the most important for long-term health outcomes [3], the nutritional status of women during pregnancy including GWG influences birth outcomes, maternal and infant health, and long-term risk for chronic disease in the mother and child [4]. Lifestyle interventions during pregnancy that aim to foster healthy GWG [5-7] may lower the risk of adverse birth outcomes and maternal [8] and childhood [9, 10] obesity. Women who are economically disadvantaged are the most vulnerable to maternal obesity [11, 12], excess weight gain in pregnancy [13, 14] and poor birth outcomes [15-18]. According to the U.S. Census Bureau, in 2015 more than one in eight women and one in four children in the U.S. lived in poverty [19]. Therefore to positively impact the health of the most vulnerable populations' to the effects of obesity there is a critical need for scalable and effective healthcare services that target GWG. The federally-funded program WIC has an unprecedented position to deliver scalable and effective lifestyle interventions in low income and nutritionally at risk pregnant women. According to CDC Pregnancy Risk Assessment Monitoring System data reports that span more than 15 years, at least 50% of the pregnant women supported by WIC are overweight or obese [20] and only 30% achieve appropriate GWG [21]. Moreover because WIC has an established national framework and supports approximately 15% of pregnancies in the US each year [22], WIC has a unique opportunity to disseminate a weight management program to millions of pregnant women.

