The sample size was changed to enroll at least 330. The COVID-19 pandemic occurred in the early stages of data collection for the trial (i.e., 9 months after the first participants was screened). This resulted in several statewide restrictions, including lockdowns (with the initial "Stay at Home Order" issued on March 22nd, 2020), after 87 participants had been screened and 26 participants were in the primary data collection phase of the trial. Study visits were continued for participants who were already in the screening process or enrolled in the trial. It was necessary for visits to be modified to allow for collection of data to occur in a manner that ensured compliance with COVID-19 mandates (e.g., social distancing, wearing of PPE, etc.) for the participant and study staff. Restrictions required recruitment to cease for 5 months (March 2020 through July 2020). Research activities resumed when Louisiana progressed to Phase 2 of the reopening plan however, multiple restrictions were still in place that required adjustment of study procedures (detailed in the amended protocol). To adjust to and address the unforeseen circumstances arising from COVID-19 (including to comply with the time constraints set by the funding institute), the trial steering committee decided in October 2022 to end enrolment by December 2023. Based on trial enrolment through 2022, enrolment rate was estimated to be at least 11 participants per month for the following year, and as a result, it was assumed that the trial could achieve a sample size range of between N=339 and N=360. See below in section 2.3 for more details.

Section 2.2

Amendment May 2024:

The randomization section edited to denote that regions were used as the blocking information for the randomization scheme as compared to clinics since multiple clinics per regions were used for enrolment.

Section 2.3

Amendment October 2022:

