We will investigate study observed GWG, weekly GWG, and deviation between the observed rates of weekly GWG and rates deemed appropriate by the 2009 IOM. Based on our pilot data (Table 3), pregnant individuals with overweight and obesity in the SmartMoms® group had comparable deviation rates (gaining an additional ~0.06 kg/week above the recommended amount) whereas the Usual Care group had a greater deviation rate that was seen in both BMI strata. With our planned sample size of at least 330 participants, we have more than 80% power to detect a difference of at least 0.16 kg/week between the SmartMoms® and Usual Care group and within each BMI category, and over 99% power to show overall differences between groups in study observed GWG.

Table 3. Weekly GWG in Expecting Success

BMI Category	Usual Care Weekly GWG Deviation Rate (kg/week)	SmartMoms® Weekly GWG Deviation Rate (kg/week)
Overweight	0.208	0.063

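### The within-BMI power for Hypothesis 1 (0.80 at 26 points) needs 110 evaluable women in every BMI category; the enrolment rule does not secure that, and Table 2 leaves out the 15% attrition

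*SAP*

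**What the plan says.** SAP 2.3.1 states for Hypothesis 1 that "110 participants in each BMI stratum are sufficient to detect a difference of at 26% in incidence within each BMI stratum". Table 2, titled "Power For Detecting Differences Within Each BMI Stratum", gives power of 0.70, 0.80 and 0.88 for differences of 23, 26 and 29 percentage points. SAP 1.4 says without qualification that the sample sizes are powered within each BMI subgroup. SAP 2.3 repeats that power is sufficient for the comparisons within BMI groups, and adds that all sample sizes are inflated for 15% attrition.

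The enrolment rule is in SAP 2.3. Enrolment runs until December 2023 or until all three categories have 110 women, whichever comes first, and "Enrolment in any given BMI category will continue past 110 if the other BMI categories have yet to meet the enrolment goal". The commitment is to a total of at least 330 with relative balance; no category has a minimum. The Section 2.1 entry in the SAP's list of amendments gives the projection: "it was assumed that the trial could achieve a sample size range of between N=339 and N=360".

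SAP 4.3 reports Hypotheses 1 and 2 within each BMI category.

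**The concern.** The power is stated for a category size that the plan sets as a target but does not guarantee, and for women evaluable rather than women enrolled. A total of 330 or more can be reached with one category below 110, and the SAP gives no power for that case. Even a category with exactly 110 enrolled loses women before the late-pregnancy weight on which the primary analysis depends.

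What is at stake is how a subgroup result is read. If one BMI category shows no significant difference, the SAP as written invites the conclusion that an adequately powered comparison found nothing. SAP 2.3 ties the within-BMI comparison to the funding announcement, so the figure is likely to be relied on.

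**Working it through.** **Inputs.**
- Category size 110, so 55 per arm at 1:1 (SAP 2.2 and 2.3.1).
- "The sample size estimates assume β =0.8 and α =0.05 to detect the specified differences" (SAP 2.3; the 0.8 is read as power). Sidedness is not stated; two-sided is assumed.
- Base rate 28.7%, the overall entry in Table 1 under "Usual Care Appropriate GWG Incidence Rate". Table 2 does not name its base rate, so this is an assumption. The category rates are 36.9%, 23.9% and 25.2%.
- Attrition 15% (SAP 2.3). Projected total 339 to 360 (list of amendments, Section 2.1).

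**Formula.** Two-proportion z-test with pooled null variance and n per arm:

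power = Φ{ [Δ√n − 1.96 √(2p̄(1−p̄))] / √(p₁(1−p₁) + p₂(1−p₂)) }

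**Step 1: reproduce Table 2.** For 26 points, p₁ = 0.287, p₂ = 0.547 and p̄ = 0.417. With n = 55 the numerator is 0.26 × 7.416 − 1.96 × 0.6973 = 0.5615. The denominator is 0.6726, so power is Φ(0.835) = 0.798. With 15% attrition, n = 55 × 0.85 = 46.75.

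| Difference | Table 2 | n = 55, no attrition | n = 46.75, 15% attrition |
|---|---|---|---|
| 23 points | 0.70 | 0.697 | 0.624 |
| 26 points | 0.80 | 0.798 | 0.729 |
| 29 points | 0.88 | 0.877 | 0.819 |

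Table 2 is therefore a calculation for 110 evaluable women. At 46.75 per arm the unpooled (0.753), arcsine (0.733) and continuity-corrected (0.653) versions also miss 0.80. With the three category base rates, power at 110 enrolled and 15% attrition is 0.72 to 0.75. Table 1 does include attrition: at 330 × 0.85 and +16 points the same formula gives 0.797. The two tables are on different bases.

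**Step 2: what a category would need.** Eighty per cent power for 26 points takes 56 evaluable per arm. That is 112 / 0.85 = 132 enrolled per category, or 396 in total with equal categories, which is above the projected 339 to 360. At 110 enrolled (93.5 evaluable) the difference with 80% power is about 28 points.

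**Step 3: does the rule deliver 110?** The smallest category must hold 110/339 = 32.4% or 110/360 = 30.6% of all women. The documents do not give the three-way BMI mix, so mixes are assumed and recruits are treated as random draws (multinomial, 200,000 draws).

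| Assumed mix | Chance all three reach 110 at N = 339 / 350 / 360 | Mean size of smallest category | Power at 26 points at that size, no attrition |
|---|---|---|---|
| Equal thirds | 12% / 40% / 65% | 104 / 108 / 111 | 0.775 / 0.79 / 0.80 |
| 40/30/30 | 1% / 4% / 12% | 96 / 99 / 102 | 0.74 / 0.75 / 0.77 |

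**Step 4: both together.** Applying 15% attrition to 96 to 102 enrolled gives power of 0.67 to 0.70, and a difference with 80% power of about 29 to 30 points.

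**The case against.** Several points on the other side are sound.

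- **No document shows a shortfall.** A reader might infer that the smallest category probably fell below 110. That depends on a BMI mix the documents do not give. The protocol's background section says only that "at least 50% of the pregnant women supported by WIC are overweight or obese", which is a floor for two categories combined; a two-thirds share split evenly would be exactly equal thirds. With equal thirds the average loss is 0 to 2 points, and a smallest category of 98 or fewer, where the loss reaches about 5 points, occurs in 14%, 6% and 2% of draws at N = 339, 350 and 360.
- **The uncapped rule is not the cause.** A reader might blame the decision to keep full categories open. With a fixed end date, closing a full category adds no one to a lagging one unless recruitment effort moves. The rule keeps the trial open so that lagging categories can fill.
- **The projection dates from 2022.** The current text commits only to at least 330, and enrolment was due to close before the May 2024 SAP.
- **Hypothesis 2 is not undermined by this argument.** For the three weight strata as well as overall, SAP 2.3.1 reads in part: "we have more than 80% power to detect a difference of at least 0.16 kg/week between the SmartMoms® and Usual Care group and within each". A reader might expect that figure to fall in the same way, but it would do so only if the SD were near 0.297, the largest value that sentence allows (80% at 55 per arm). Protocol 12.2 claims more than 80% power for 0.12 kg/week within each category at 432 women. At 72 per arm this bounds the SD at about 0.255. Power for 0.16 kg/week is then 0.90 at 110 and 0.815 at 85, without attrition. If the protocol figure already allows for attrition (about 61 per arm), the bound is 0.235; after 15% attrition power is still 0.90 at 110 enrolled and 0.81 at 85.

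None of this answers the two points that remain: 110 is a goal stated as if it were secured, and Table 2 omits attrition.

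**Conclusion.** The within-BMI power for Hypothesis 1 is overstated as written. The firmer part needs no assumption about BMI mix: by the SAP's own attrition, 110 enrolled gives about 0.73 at 26 points (0.72 to 0.75 across the category base rates), not 0.80. This rests on a two-sided pooled z-test and a 28.7% base rate, which together reproduce all three Table 2 entries.

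The second part is conditional. The plan does not secure 110 per category and gives no power for a smaller one. The cost before attrition runs from nothing to about 2 points with equal thirds, and from about 3 to 6 points at an assumed 40/30/30. Whether a category actually fell short cannot be settled from the documents. The point concerns the subgroup claim for Hypothesis 1 only; it gives no ground for changing the Hypothesis 2 power sentence.

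**What to change.** 1. In SAP 2.3 and 2.3.1, describe 110 per BMI category as an enrolment goal, not as a number the rule guarantees.
2. Recalculate Table 2 for each BMI category at its actual evaluable number, meaning women with both an early and a late clinic weight. Pool the arms so that nothing is unblinded. Add the difference with 80% power for the smallest category, and state the base rate and sidedness used.
3. If evaluable counts were not complete at the SAP date, use actual enrolled × 0.85. This is possible: a woman enrolled at 10 weeks in December 2023 could have her late visit up to about 28 weeks afterwards, in July 2024.
4. Amend the power sentences in SAP 1.4, 2.3 and 2.3.1 to match the new table.

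The cost is one recalculated table and a few sentences, with less favourable subgroup power on the page. No new participants or data are needed. If every category did reach 110, reporting the counts settles the enrolment question and leaves only the attrition correction.
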